# 10.1 Overall Study Design and Plan

The study will be conducted in three parts (Part A, Part B and Part C).

- Part A of the study is a single centre, double-blind, randomised, placebo-controlled, parallel-group, multiple oral dose, dose-escalation study to assess the safety, tolerability and PK of DNDI-0690 after multiple oral doses in the fasted condition in healthy male and woman of non-childbearing potential (WONCBP) subjects.
  - Part A will consist of up to 4 cohorts of 9 subjects. Subjects will be randomly assigned to receive an oral dose of active IMP (6 subjects) or matching placebo (3 subjects) for 10 days in a sequential escalating manner with a minimum of 7 days interval between two cohorts.
  - o In Part A, each cohort will follow a sentinel dose-escalation schedule according to European Medicine Agency (EMA) guideline; two (2) subjects will be dosed on the first dosing day of EACH cohort (1 subject on active IMP and 1 subject on matching placebo). The remainder of the cohort (5 subjects on active IMP and 2 subjects on matching placebo) will be dosed a minimum of 48 hours later pending confirmation of an acceptable safety profile in the dose-leader cohort by the PI, or medically-qualified designees who are familiar with the study protocol and IB.
- Part B of the study is a single centre, double-blind, randomised, placebo-controlled, multiple oral dose study to assess the pharmacodynamic effect of DNDI-0690 on cardiac function after multiple oral doses at the supra-therapeutic dose in fasted condition in healthy male and WONCBP subjects. Part B is optional.
  - Part B will consist of 1 cohort of 9 subjects. Subjects will be randomly assigned to receive an oral dose of active IMP (6 subjects) or matching placebo (3 subjects) for 5 days. Part B will only be implemented if the SRC considers it safe and appropriate to proceed to dose-escalation (with a maximum considered dose of 3600 mg).
  - O Subjects in Part B will follow a sentinel schedule; two (2) subjects will be dosed on the first dosing day (1 subject on active IMP and 1 subject on matching placebo). The remainder of the cohort (5 subjects on active IMP and 2 subjects on matching placebo) will be dosed at least 48 h later pending confirmation of an acceptable safety profile in the dose-leader cohort by the PI, or medically-qualified designees who are familiar with the study protocol and IB.

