Steady state is expected to be reached within 3 days maximum based on the observed geometric mean  $t_{1/2}$  (ranging from 4.547 to 12.144 hours, depending on doses). Based on the minimally acceptable duration of VL treatment of 14 days as per the VL Combination therapy Target Product Profile, the duration of the present repeated dosing study was chosen to be 10 days. As steady state will likely be reached in 3 to 4 days, a duration of 10 days seems sufficient to describe the safety profile of DNDI-0690 in healthy volunteers.

Reversible and non-clinically relevant elevations of the creatinine levels were identified in healthy volunteers during the SAD. This pattern of slight increase in creatinine may be explained by an inhibition of creatinine secretion by cellular transporters. DNDI-0690 was assessed *in vitro* against a panel of drug transporters, showing 27.4 and 55.1 % inhibition of multidrug and toxin extrusion1 (MATE1; expressed in human embryonic kidney (HEK) cell line) at concentrations of 1 and 10  $\mu$ M DNDI-0690, respectively. This effect could explain the

DNDi RD 777/34920 DNDi- 0690- 02

Final V3.0/ Date 07 December 2020

Confidential

Page 52 of 109

moderate increase in plasma creatinine which was observed in the SAD study. Of notice, MATE2 was unaffected in the *in vitro* studies.

Proper follow-up of renal function in the MAD, including the monitoring of plasma creatinine, BUN and biomarkers not affected by enzymatic transporters such as Cys C, will be ensured. A specific exploration of the renal function is proposed in part C of the MAD study with administration of iohexol, a non-ionic contrast agent used as marker freely filtrated by the glomerulus, and measure of its plasma clearance in order to establish the GFR in placebo and DNDI-0690 treated healthy subjects.

Dose escalation between cohorts will be limited to a 2-3-fold increase depending on safety and tolerability data and predicted exposure (both AUC and  $C_{max}$ ).

The highest scheduled dose in Part A is set to 2400 mg/day. In addition, if safety stopping criteria are not met, a higher dose may be considered (up to a maximum of 3600 mg/day) for assessment of QT, but likely based on a shorter duration of treatment (see below Part B).

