  - Ae%: % of dose excreted in urine over each collection interval (0 to 24 h post-dose).
  - CLR: Renal clearance

If BID dosing, AUC0-10, AUC0-10/D, AUC0-10h,norm will be added on Day 1 and Day10.

Derived PK parameters will be listed along with the points used to calculate  $k_{el}$  (lower, upper and number used) and  $R^2$  adjusted. The derived PK parameters will also be summarised. The descriptive statistics presented will be N, n, arithmetic mean, geometric mean (with the exception of  $T_{max}$ ), SD, coefficient of variation (CV%), minimum, median and maximum.

**Dose Proportionality/Independence (Part A and Part B):** For Day 1 and Day 10 (Part A) OR Day 1 and Day 5 (Part B), dose proportionality will be assessed by performing a regression analysis of the log-transformed  $C_{max}$ ,  $AUC_{0-\tau}$  and  $AUC_{0-inf}$  (Day 10 for Part A and Day 5 for Part B only) values versus the log-transformed dose using the power model with a fixed effect for log(dose). For each parameter a point estimate and 95 % confidence interval (CI) will be calculated for the slope of the regression line.

For Day 10 for Part A and Day 5 for Part B, dose independence will be assessed for t½ and CL/F by performing a regression analysis of the untransformed parameters versus dose with a fixed effect for dose. For each parameter a point estimate and corresponding 95 % CI will be calculated for the slope of the regression line.

**Steady-State** (**Part A and Part B**): For each dose level, log-transformed trough concentration levels at pre-dose each day (Day 2 to Day 10 for Part A and Day 2 to Day 5 for Part B) will be subjected to a mixed effects analysis of variance (ANOVA) with study day as a fixed effect and subject as a random effect in order to establish whether and when steady-state has been attained for each dose level. Back-transformed ratios for the comparisons of each consecutive day (*i.e.* Day 3/Day 2) will be presented along with corresponding 90 % CI.

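### Consecutive-day trough ratios are a low-power way to establish when steady state is reached; comparing each day with the mean of later days answers the question better from the same data and model

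*Protocol*

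**What the plan says.** The method is in Section 10.9.2.5.4 (PK Data, Steady-State) and is repeated in the Synopsis. For each dose level, log-transformed pre-dose troughs ("Day 2 to Day 10 for Part A and Day 2 to Day 5 for Part B") go into a "mixed effects analysis of variance (ANOVA) with study day as a fixed effect and subject as a random effect". The stated purpose is "in order to establish whether and when steady-state has been attained for each dose level". The contrasts are "Back-transformed ratios for the comparisons of each consecutive day", with Day 3/Day 2 as the example, and they "will be presented along with corresponding 90 % CI". That makes eight ratios in Part A and three in Part B. No other contrast is named, and no rule says how the ratios lead to a conclusion.

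Each Part A cohort, and the Part B cohort, is randomised to an "oral dose of active IMP (6 subjects) or matching placebo (3 subjects"), so a dose level contributes 6 subjects to this analysis. Section 10.3.1 states "Steady state is expected to be reached within 3 days maximum", based on geometric mean half-lives "ranging from 4.547 to 12.144 hours, depending on doses". A separate accumulation analysis compares Day 10 (Part A) or Day 5 (Part B) with Day 1 for Cmax and AUC over the dosing interval.

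**The concern.** A consecutive-day ratio asks whether today differs from yesterday. The stated question is from which day troughs sit on the plateau. When troughs approach a plateau in shrinking steps, each ratio carries only one step of the remaining rise, and its standard error comes from two days although the other days also inform the plateau. With 6 subjects, a ratio can have a CI that includes 1 while the earlier day is still well short of plateau.

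What is at stake is the reported day of onset of steady state at each dose level. Part B has only four trough days, so there is less room to see the plateau there.

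**Working it through.** **Inputs from the protocol.** n = 6 active subjects per dose level; trough Days 2 to 10 (Part A) and 2 to 5 (Part B); 90% CIs; half-lives 4.547 to 12.144 h.

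**Assumptions.** Once-daily dosing, one-compartment accumulation, a common half-life, independent within-subject errors, and a within-subject trough CV of 15% to 40%. The protocol does not give this CV.

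**The protocol's own figure.** Five half-lives at the longest value are 5 × 12.144 = 60.7 h, or 2.53 days. At 72 h the fraction of steady state is 1 − 2^(−72/12.144) = 98.4%. The expectation of 3 days at most is reproduced.

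**Expected troughs.** With q = 2^(−24/t½), the Day d trough is proportional to (1 − q^(d−1))/(1 − q), and its fraction of plateau is 1 − q^(d−1).

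- At 12.144 h, q = 0.254. The Day 2, 3, 4 and 5 troughs are 74.6%, 93.5%, 98.4% and 99.6% of plateau. The consecutive ratios are 1.254, 1.052, 1.012, then about 1.00. From Day 2 the remaining rise is 1/0.746 = 1.34, or 34%, of which Day 3/Day 2 shows 25%.
- At 4.547 h, q = 0.026 and the Day 2 trough is already 97.4% of plateau.

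**Standard errors on the log scale**, with s = √ln(1 + CV²):

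- Consecutive days: s·√(2/6) = 0.577s.
- Day 2 against the mean of Days 3 to 10: s·√((1 + 1/8)/6) = 0.433s, which is 0.75 times the consecutive value.
- Day 2 against the mean of Days 3 to 5: s·√((1 + 1/3)/6) = 0.471s, which is 0.82 times.

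Residual degrees of freedom are 8 × 5 = 40 in Part A (t = 1.684) and 3 × 5 = 15 in Part B (t = 1.753).

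**Example, Part A, CV 20%.** s = 0.198. Consecutive: ln 1.254 = 0.226, SE 0.114, expected 90% CI 1.03 to 1.52. Helmert: the expected ratio at Day 2 is 1.326, ln 1.326 = 0.282, SE 0.086, expected 90% CI 1.15 to 1.53.

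**Probability that the 90% CI lies wholly above 1 at Day 2, half-life 12.144 h** (noncentral t; simulation agrees to within about one percentage point):

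| CV | Part A, Day 3/Day 2 | Part A, Day 2 vs 3–10 | Part B, Day 3/Day 2 | Part B, Day 2 vs 3–5 |
|---|---|---|---|---|
| 15% | 83% | 100% | 81% | 97% |
| 20% | 62% | 94% | 60% | 85% |
| 30% | 37% | 70% | 36% | 57% |
| 40% | 26% | 51% | 25% | 40% |

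**If a CI containing 1 at the Day 2 contrast were taken as steady state** (a reading the protocol does not state), Day 2 would be chosen in 18%, 38%, 63% and 73% of Part A trials at CVs of 15%, 20%, 30% and 40% with the consecutive ratio, against 0.4%, 6%, 30% and 49% with the Helmert contrast.

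**A rule to avoid.** Suppose steady state were the first day from which that contrast and all later ones have CIs including 1. With no drift at all, at least one of the eight Helmert CIs excludes 1 in about 55% of simulated Part A trials, so a true Day 2 onset would be rejected that often.

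**The case against.** The strongest reply is that the protocol only says the ratios will be presented. It contains no rule that a CI including 1 means steady state, and the Synopsis leaves analysis details to the SAP, which is not at hand. That stands: a reader might infer that steady state will be declared from Day 2, but the document does not say so. The early-onset risk is therefore conditional on how the ratios are read. The choice of contrast, however, is made in the protocol.

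Three other strong readings are tempting and not supported.

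- *Consecutive ratios cannot detect accumulation.* They can. Under first-order accumulation the first step is the largest, and it is detected in 26% to 83% of Part A trials over the CV range. The problem is low power.
- *A slow daily creep would go unseen.* A constant 5% rise per day at CV 20% would widen the gap to 13% against 81%. But under first-order kinetics a Day 3/Day 2 ratio of 1.05 means q = 0.05, a half-life of about 5.6 h and a total further rise of about 5%. Sustained creep conflicts with the documented half-lives and the 3-day expectation. It would need kinetics that change over time; the predictions in Section 10.3.1 assume linearity over time, and the human data behind them are single-dose.
- *The Day 10 or Day 5 parameters depend on this analysis.* They are computed on fixed days regardless, as are the accumulation ratios.

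The accumulation analysis also shows overall accumulation, but not when it ended. The study calls itself exploratory and has no formal sample size, which limits the importance of the point without removing it.

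**Conclusion.** The concern holds as a matter of efficiency and fit to purpose. The protocol sets out to establish when steady state is attained and names only contrasts that see one step at a time. At the longest documented half-life, with troughs 25% below plateau on Day 2, power at that day in Part A is 62%, 37% or 26% (CV 20%, 30%, 40%), against 94%, 70% or 51% for the comparison with later days. In Part B it is about 60%, 36% or 25% against 85%, 57% or 40%. At 4.547 h the Day 2 shortfall is under 3% and the choice of contrast hardly matters.

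These figures rest on the assumed CVs, once-daily dosing, one compartment and a common half-life; twice-daily cohorts would differ. The 12.144 h is a geometric mean, so some subjects will be slower. As a secondary PK analysis, this is of minor to moderate importance.

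**What to change.** Keep the mixed model and add Helmert contrasts, alongside or in place of the consecutive-day ratios: each day against the geometric mean of all later days. In Part A these run Day 2 vs 3–10, Day 3 vs 4–10 and so on; in Part B, Day 2 vs 3–5, Day 3 vs 4–5 and Day 4 vs 5. The last contrast in each part is the same as the consecutive one, so the gain is in the early days, where it is needed.

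State that steady state is judged from the size of the estimated ratios and their 90% CIs, not from whether a CI includes 1. Do not adopt a rule that all later CIs must include 1, given its roughly 55% rejection of a true Day 2 onset in Part A.

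The cost is a change of wording in Section 10.9.2.5.4 and the Synopsis, carried into the SAP, and slightly more analysis and output. No further samples, visits or subjects are needed.

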#### 10.9.2.5.5 PD Data

N/A.

#### 10.9.2.5.6 Other Data

- mGFR will be calculated following evaluation of plasma clearance of iohexol before and under exposure to DNDI-0690. mGFR data will be descriptively analysed together with their 95% confidence intervals. More details on methodology will be provided in the SAP.
- Exploratory Endpoints:
  - Changes in clinical early renal toxicity markers in urine: Cystatin C (Cys C), Kidney Injury Molecule-1 (KIM-1), neutrophil gelatinase-associated lipocalin (NGAL).
  - Analysis of Holter extracted ECGs for the following parameters: RR, heart rate (HR), PR, QRS, QT, corrected QT interval by Fridericia's formula (QTcF), corrected QT interval by Bazett's formula (QTcB), ΔHR, ΔRR, ΔPR, ΔQRS, ΔQT, ΔQTcF and ΔQTcB.
  - Measurement of drug concentration in dry blood spots for comparison with matching plasma samples
  - Variation of mRNA expression in blood sample before and after exposure to the drug (Transcriptional Profiling)
  - o Exploration of metabolism after multiple dose exposure

#### 10.9.3 Sample Size Calculation

The study is exploratory. The sample size chosen for this study is not based on a formal statistical estimation but is considered to be adequate to meet the objectives of the study. Based on experience from previous studies of a similar design, a total of 9 subjects are to be enrolled per cohort and a minimum of 6 evaluable subjects per cohort are considered sufficient.

A sufficient number of subjects will be initially screened for enrolment to ensure that the planned sample size is achieved.

Confidential

Final V3.0/ Date 07 December 2020

Page 105 of 109

#### 11 PRACTICAL CONSIDERATIONS

# 11.1 Storage of Data

**DNDi** 

RD 777/34920

DNDi- 0690- 02

The ISF and associated study documentation will be archived for at least 25 years after the end of the study (last participant last visit) as per EMA Guideline INS/GCP/856758/2018. The study documentation may be transferred to an offsite storage facility during this period but will remain under the control of Simbec-Orion.

The Sponsor's electronic trial master file (eTMF) will be used during the study. Sponsor will be responsible for the setup of eTMF. Sponsor has delegated the maintenance of the Sponsor eTMF to Simbec-Orion. The eTMF will be archived by Sponsor for at least 25 years after the end of the study.

## 11.2 Protocol Amendments

Changes in the study protocol must take the form of written protocol amendments and shall require the approval of all persons responsible for the study (see Section 1).

A protocol amendment is deemed to constitute a substantial protocol amendment if it is considered to be likely to affect to a significant degree either:

- a. The safety or physical or mental integrity of the subjects of the study.
- b. The scientific value of the study.
- c. The conduct or management of the study.
- d. The quality or safety of any IMP used in the study.

Such amendments must be submitted to the REC responsible for the study and the MHRA for approval prior to implementation.

Substantial protocol amendments required for urgent safety reasons may be implemented immediately. However, the REC and MHRA must be notified in writing within 3 days of the measures taken and the reasons for implementation.

All other amendments shall be deemed to be non-substantial and as such do not need the prior approval of the REC and the MHRA.

# 11.3 Confidentiality

The confidentiality of the study must be maintained at all times and the PI must not reveal any information relating to the study without express permission from the study Sponsor.

## 11.4 Study Report and Publication Policy

Simbec-Orion will investigate and analyse the data generated with all due speed.

A draft study report will be sent to the Sponsor for review. The Sponsor will forward any comments on the draft study report to the Project Manager within 30 days of receipt. Additional review cycle may be implemented if deemed necessary by the Sponsor. Upon receipt of these comments a final, QA approved report will be issued with all due speed. A copy of the report will be forwarded to the Sponsor.

Confidential

Final V3.0/ Date 07 December 2020

Page 106 of 109

The PI will obtain the Sponsor's written permission before any information concerning this study is submitted for publication.

# 11.5 General Data Protection Regulation (GDPR)

**DNDi** 

RD 777/34920

DNDi- 0690- 02

Personal data of the volunteer shall be processed in a manner that ensures it has appropriate security. This includes protection against unauthorised or unlawful processing and against accidental loss, destruction or damage and by using appropriate technical or organisational measures. One such measure is by the Investigator ensuring that the volunteers' personally identifiable information should be replaced through the use of pseudonymisation.

On the eCRFs or other documents submitted to DNDi/Simbec-Orion volunteers will NOT be identified by their names but by the assigned volunteer number (panel/screening/subject number) to ensure confidentiality of the volunteers' information and that data minimisation principles are maintained. If volunteer names are included in error on copies of documents submitted to DNDi/Simbec-Orion volunteers', the names and initials will be erased or securely destroyed, and the assigned volunteer number added to the document.

Confidential

Final V3.0/ Date 07 December 2020

Page 107 of 109

**DNDi** 

Final V3.0/ Date 07 December 2020

Page 108 of 109

# APPENDIX 1: NORMAL RANGES FOR VITAL SIGNS AND ECG PARAMETERS

Vital Sign Parameters				
Pulse Rate	50-100 Beats per minute (bpm)			
Systolic Blood pressure	90-140 mmHg			
Diastolic Blood pressure	50-90 mmHg			
Tympanic Temperature	35.0-37.5 Degree Celsius			

ECG Parameters				
Heart Rate (HR)	50-100 bpm			
PR Interval	120-220 ms			
QRS Width	70-120 ms			
QT Interval	≤ 500 ms			
QTc Interval- Bazetts' (QTcB)	350-450 ms			
QTc Interval -Fredericia's (QTcF)	350-450 ms			

Final V3.0/ Date 07 December 2020

Confidential

Page 109 of 109

# APPENDIX 2: DECLARATION OF HELSINKI (BRAZIL, 2013)

https://www.wma.net/policies-post/wma-declaration-of-helsinki-ethical-principles-formedical-research-involving-human-subjects/
